### **Time-to-event variables**

Survival analysis will be used to assess “time to an event” variables, for example, treatment retention. Survival analysis can be used to assess whether the incentive or usual care group differ in assessing time to the last face-to-face contact. We define the “event” of interest as “leaving treatment.” Leaving treatment is defined as occurring whenever a subject fails to complete the entire treatment period. The log rank test or Cox proportional hazard models will be used to identify a difference between the treatment and control groups. Cox regression will be used to test whether other independent variables affect retention. The primary statistic of interest will be hazard ratios with 95% confidence intervals.

### **Continuous and dichotomous summary variables**

For summary variables using continuous data (e.g. percent of negative urines; longest duration of abstinence), we will use t-tests for simple analyses and multiple regression if it is necessary to control for baseline or other covariate differences. For summary variables using dichotomous data (e.g., percent of patients achieving 30-day abstinence at follow-up or achieving 4 or 8 weeks of abstinence during treatment), we will use chi square with relative risks and 95% confidence limits for simple comparison of treatment groups. If it is necessary to control for covariates, logistic or Poisson regression will again be used.

### **Repeated measures variables**

For continuous variables that are measured either during treatment (e.g. at each follow-up time point), classical repeated measures analysis of variance would be possible if missing data is non-existent or minimal. If missing data is a problem, then methods of analysis used for mixed linear models will be used. These methods allow for missing data with repeated measures. For continuous or dichotomous variables measured at several time points (e.g. follow-up outcomes), we propose using GEE. GEE is a powerful analytic method that is used to correct for correlation among observations within subjects in a repeated measures design. Odds ratios and 95% confidence limits will be produced to represent differences between the treatment groups and to estimate the effects of other variables. It may be possible that there is decay over time in treatment effects. Focusing on only one time point (e.g. end-of-treatment), we propose to compare treatment and control groups using chi square and compute relative risk and 95% confidence limits. To adjust for covariates and possible site differences, logistic regression analysis will be used to assess treatment effects. While logistic regression provides accurate estimates of statistical significance, the method tends to produce inflated estimates of risk when prevalence of an outcome is high. Poisson regression may be used to produce more accurate estimates of risk relative risk).

## **16.5 Other statistical issues**

### **Replacement of missing data**

In general, data replacement should not be necessary since statistical techniques have been selected that accommodate data sets with missing data. For the measure “longest duration of abstinence”, a single missed urine/breath test will be tolerated and replaced by a negative result if both surrounding tests for that drug are negative. In all other cases (one or both surrounding tests are positive for that drug or more than one consecutive test is missing), the sample result is replaced by a positive.

### **Baseline Comparability of Sites**

It is important to evaluate the comparability of sites with respect to potential confounders. Categorical methods of analysis (e.g. cross tabulations, chi-square) will be used to compare sites for qualitative data. ANOVA will be used to test for homogeneity of the sites for continuous data. If a statistically significant difference is found, a “site” term will be included in any subsequent analysis. If sufficient power exists, we may perform stratified analysis by sites.

### **Baseline Comparability of Treatment and Control Groups**

Categorical methods of analysis (e.g. cross tabulations, chi-square) will be used to compare treatment and control groups for qualitative data. T-tests will be used to test for homogeneity of the treatment groups for continuous data. If a statistically significant difference is found, terms representing the covariate will be included in any subsequent analysis.

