## **9 PROJECTED STUDY SAMPLE SIZE: 400**

One perspective on sample size was obtained by conducting a power analysis based on data from Piotrowski et al. (1999). This study implemented a complex incentive intervention at a community VA methadone clinic that targeted multiple drugs of abuse. Although the specific intervention was quite different from the one proposed in the current CTN protocol, this was an incentive study conducted in a community clinic with considerable variability in outcome. With probability of a Type I error set at 0.05 (alpha) and a Type II error set at 0.20 (Power = 0.80), and using a two-tailed test, it was determined that 130 subjects would be needed in the incentive and control groups, respectively, to obtain statistical significance on the measure percent drug negative urines (28.5% versus 16.3% during months 5 and 6).

Additional sample size estimates have been calculated based on two recently published voucher incentive studies, one of which did (Preston et al., 2000) and one of which did not (Downey et al., 2000) detect statistically significant effects of the voucher intervention being tested. Effect sizes for the primary outcome variable percent drug-free urines ranged from .16 to .19 with a mean of .18. This yielded sample size estimates of 110-153. In addition, these estimated sample sizes have been adjusted based on 10% to 20% increases in variability due to multi-site testing. As shown in the appended table, our projected sample size of 200 per group should allow us to detect between group differences of the magnitude previously observed with power = .80 and alpha = .05, even with a 20% increase in variability over single-site studies.

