## 11.2 Study intake procedures for methadone clinics

Methadone clients will not begin the study until week 5 of treatment or later. It is anticipated that regular (at least biweekly) urinalysis results will be available during this time. Those eligible for the study will have at least one cocaine or methamphetamine positive urine documented during the two weeks prior to study intake.

Clients are approached for study intake by RA's or counselor. The study opportunity will be described to eligible enrollees. Those interested in participation will be escorted to the study intake site. RA or designated counselor will perform the following procedures:

1. Describe study
2. Obtain informed consent
3. Conduct common assessment intake battery (see section 14)
4. Conduct stratification

Subjects will be stratified on two variables prior to random assignment:

- a) presence versus absence of any target stimulant drug in urine
- b) presence versus absence of bonus drug (opiate) in urine.

5. Conduct randomization

Randomization will take place at each site independent of other sites. Thus, stratification by site is not necessary. Stratification and random assignment will be computerized using the dynamic balanced randomization procedure (Signorini et al., 1993).

6. Conduct incentive procedure for those clients assigned to incentive condition who test drug-negative at intake. Remind these clients when they will be eligible for their next recovery pick
7. Discuss urine results in relation to study procedures:

Those in incentive condition testing drug negative will be encouraged to remain negative and reminded of the subsequent recovery pick opportunities.

Those in incentive condition testing drug positive will be encouraged to stop using so they can earn recovery picks as soon as possible and reminded that they can begin earning picks the next time they come into the clinic.

Those in no incentive condition will be encouraged to become or remain drug-free in order to take full advantage of their time in treatment .

8. Allow clients to choose one large incentive for intake bonus.
9. Initiate caserecord for new participant; enter intake data

Whenever possible, all procedures will be completed on the day the client is approached about study participation. If necessary, clients can return the following day to finish intake. In this case, another urine will be collected for use as the first study urine, and this will be counted as the study intake day.

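### Covariates enter the analysis only after a significant baseline difference between arms, a rule that will almost never select the two urine results used to stratify randomisation.

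*Protocol*

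**What the plan says.** Section 11.2 of the protocol fixes the design: "Subjects will be stratified on two variables prior to random assignment". The two variables are presence of a target stimulant and presence of an opiate in the intake urine. It adds that "Randomization will take place at each site independent of other sites" and concludes that site need not be a stratification variable. Site is therefore in effect a third stratum.

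Section 16.4 (Continuous and dichotomous summary variables) gives percent negative urines and longest abstinence as its examples of continuous summary measures. These correspond to the two primary during-study outcomes in section 16.1. For such measures, "we will use t-tests for simple analyses and multiple regression if it is necessary to control for baseline or other covariate differences". Dichotomous measures get a chi-square test with relative risks, and regression if covariates must be controlled.

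Section 16.5 supplies two triggers for adjustment:

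- **Between arms** (Baseline Comparability of Treatment and Control Groups): "If a statistically significant difference is found, terms representing the covariate will be included in any subsequent analysis".
- **Between sites** (Baseline Comparability of Sites): if the sites differ significantly from one another, a site "term will be included in any subsequent analysis".

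The protocol nowhere names the two stratification factors as terms in an analysis model.

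**The concern.** In a randomised trial, a significant baseline difference between arms reflects chance, and it says nothing about whether the variable predicts the outcome. Here the rule also works against the design. The intake stimulant result is plausibly the baseline variable closest to the primary outcomes. Stratification holds it level between arms, so a test for a difference between arms has almost nothing to detect.

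Two things are at stake. First, a t-test that ignores balanced prognostic factors leaves their variance in the error term although the design has already removed it from the comparison. The reported standard error is then too large, confidence intervals are too wide and power is forgone. Second, the list of covariates in the primary model is not known until the baseline data have been tested.

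**Working it through.** **Inputs from the protocol (section 9).** Two-sided alpha 0.05, power 0.80, effect sizes 0.16 to 0.19 (mean 0.18), 200 per group, and an allowance of 10% to 20% more variability for multi-site testing.

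**Input not in the protocol.** R², the share of outcome variance explained by the omitted balanced factors. It is assumed to lie between 0.05 and 0.30.

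**Step 1: the plan's own figure.** The metric of the effect size is not stated. Read as Cohen's f (standardised difference d = 2f), n per group = 2(1.96 + 0.842)² / (2f)²:

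- f = 0.16: 15.70 / 0.1024 = 153.3
- f = 0.19: 15.70 / 0.1444 = 108.7 (110 with the t distribution)

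This reproduces the stated 110–153. Read as d, the same values would need 435 to 614 per group, so f is the reading that fits.

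**Step 2: effect of omitting balanced factors from the t-test.** When the factors are balanced, the true standard error is √(1−R²) times the one the t-test reports. With noncentrality 1.96 + 0.842 = 2.80 for a nominal 80% design:

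- Actual type I error = 2[1 − Φ(1.96/√(1−R²))]
- Power, unadjusted = Φ((2.80 − 1.96)/√(1−R²))
- Power, adjusted = Φ(2.80/√(1−R²) − 1.96)

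| Assumed R² | Reported SE / true SE | Type I error | Power, unadjusted | Power, adjusted | Points forgone |
|---|---|---|---|---|---|
| 0.05 | 1.03 | 4.4% | 80.6% | 82.0% | 1.4 |
| 0.10 | 1.05 | 3.9% | 81.2% | 84.0% | 2.8 |
| 0.20 | 1.12 | 2.8% | 82.7% | 87.9% | 5.2 |
| 0.30 | 1.20 | 1.9% | 84.3% | 91.8% | 7.5 |

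**Step 3: the least favourable case in section 9.** Take f = 0.16, 200 per group, and the 20% allowance read as a standard deviation 1.2 times as large (an assumption). The noncentrality is 0.32 / (1.2 × √(2/200)) = 2.67. Over R² of 0.05, 0.10, 0.20 and 0.30, power is 76.6%, 77.2%, 78.5% and 80.1% unadjusted, against 78.1%, 80.3%, 84.6% and 89.0% adjusted.

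**Step 4: does the between-arm trigger select the stratifiers?** Trials were simulated with 4 sites of 100 and permuted blocks of 4 within site and both urine strata. This stands in for the dynamic procedure named in section 11.2. There were 1,500 trials in each of three scenarios, with assumed moderate prognostic strength.

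- Neither stratification factor was flagged in any trial.
- The unadjusted standard error averaged 1.12 times that of a model with both factors and site.
- Type I error was 3.1% and 2.5% unadjusted in the two null scenarios, against 5.5% and 4.5% adjusted.
- Power was 85% unadjusted and 89% adjusted.

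**Step 5: does the between-site trigger fire?** In the same simulation, with 10 assumed baseline variables, at least one site comparison was significant in 38% of trials when sites did not truly differ, and in 100% when they differed moderately.

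**Step 6: chance selection.** If 20 independent baseline variables were tested at 0.05, the chance of at least one false flag would be 1 − 0.95²⁰ = 64%. The protocol gives no count and the variables are likely to be correlated, so this is only an illustration.

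**The case against.** Most of the case against concerns stronger readings, and it succeeds against them.

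- **Site is left out.** A reader might infer this from the two triggers, but the site trigger compares sites with each other. Balancing arms within site does not make the sites alike, so across community clinics the test would probably be significant and the term would enter. Section 16.4 (Repeated measures variables) also plans logistic regression for covariates and possible site differences at a single time point, with no significance test attached there.
- **The trial is underpowered, or its false-positive risk is raised.** Neither follows. The error is conservative. In Step 2 the unadjusted test stays at or above its nominal 80%; what is lost is the extra power that adjustment would give. At the mean effect of 0.18 with a standard deviation 1.2 times as large, power at 200 per group is about 85% before any adjustment. The estimated difference in means is not biased.
- **The loss is large.** R² is an assumption. If site enters through its own rule, only the variance explained by the two urine results is forgone. At R² of 0.05 the loss is trivial.
- **The same arithmetic covers binary outcomes.** It does not. In a logistic model, omitting prognostic factors pulls the odds ratio towards 1 rather than enlarging its standard error. Power is still lost, but no figure is given for it here.
- **Covariates are chosen on results.** The trigger uses baseline data only, not outcomes.

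It can also be said that a covariate list is commonly left to a statistical analysis plan, which is not at hand and may settle the matter. In addition, the wording of section 16.4 does not itself confine adjustment to flagged variables. Both points stand, and they limit how sure one can be that the factors would be omitted. They do not rescue the rule in section 16.5, which is stated affirmatively and suits this design badly.

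**Conclusion.** The point holds for the two urine stratification factors. As written, the between-arm trigger would in practice leave them out and could admit unimportant variables by chance. For the continuous primary outcomes this makes the t-test conservative: type I error of about 4.4% to 1.9% instead of 5%, and about 1 to 8 power points forgone at a nominal 80% design, for an assumed R² of 0.05 to 0.30. These figures rest on that assumption and on close balance of the factors.

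For site the point is narrower. Its inclusion is conditional and probable, but a unit within which patients are randomised should not depend on a significance test.

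This is a worthwhile gain in efficiency and prespecification, not a threat to the validity of a positive result.

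**What to change.** Replace both triggers in section 16.5 with one fixed rule: every primary during-treatment and follow-up comparison includes intake stimulant result, intake opiate result and site, whatever the baseline tests show.

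- **Percent negative urines and longest abstinence:** linear regression with these terms.
- **Binary outcomes:** a covariate-adjusted relative-risk model, such as the Poisson regression already named in section 16.4, with robust standard errors. This keeps the effect measure the protocol prefers and respects its caution about logistic regression when an outcome is common.
- **Repeated follow-up outcomes:** the GEE already planned, with the same terms.
- **Baseline comparisons of arms and of sites:** description only.
- **Unadjusted t-tests and chi-square tests:** sensitivity analyses.

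The cost is one paragraph of wording. No new data are needed, because both urine results and site are already recorded for randomisation. With four sites, the model spends 2 + 3 = 5 extra parameters on a projected 400 participants.

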## **17 STUDY HYPOTHESES**

### **17.1 Primary hypotheses: During treatment data**

- 1) Incentive participants will have a higher percentage of urines testing negative for cocaine and methamphetamine than no incentive (as percent of urines collected; as percent of expected urines).
- 2) Incentive participants will have longer average durations of documented cocaine and methamphetamine-free urines than no incentive participants.

### **17.2 Primary hypothesis: Follow-up data**

A higher percentage of incentive than no incentive participants will have verified abstinence from cocaine or methamphetamine (negative urine and no use reported in past 30 days)

### **17.3 Secondary hypotheses: During treatment data**

- 1) Incentive participants will have longer treatment retention than no incentive participants.
- 2) Incentive participants will have a higher percentage of urine and breath tests negative for all other drugs of abuse (opiates, marijuana, and alcohol combined) during the study compared with no incentive (as percent of urines collected; as percent of expected urines)
- 2) Incentive participants will receive a higher mean number of counseling hours per week than no incentive participants.

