## **7 CTP ELIGIBILITY CRITERIA:**

In order to enter the study, clinics must have:

1. Projected average intake rate of at least 2 eligible study clients per week.
2. Projected minimum of 100 study clients to be enrolled at the site within one year.
3. Adequate space to accommodate research assistants and study protocol procedures including on-site urinalysis collection and testing.

4. Able to provide records of counseling attendance by individual clients (or institute system to obtain these data).

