### ***Recovery pick methods***

Study subjects should pick a chit from the bowl the appropriate number of times for each drug-free urine submitted. A computer program supplied by CTN will assist staff in determining the correct number of recovery picks based on history of drug-free tests. Whenever possible, these recovery pick events should take place in the presence of the study client’s counselor. RA or designated counselor is responsible for recording the results of the pick procedure, for delivering the appropriate incentive and for recording the incentive(s) selected. Clients initial or sign for each incentive received.

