### **15.2 Counseling utilization**

The research assistant, in collaboration with project coordinator and clinic staff, will be charged with setting up a system to track counseling utilization. The data desired is number of individual (15 minutes or more) and group counseling contacts per week for each study subject. Ideally, the clinic will already have a system for tracking this utilization data. In cases where a utilization tracking system is not currently in place, models will be suggested based on systems used in other participating CTP's.

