### **Counseling utilization**

Total number of group and individual sessions received  
Mean number of group and individual sessions per week during weeks of participation

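### The counseling hypothesis is stated in hours that the protocol does not collect, and its only per-week outcome divides by weeks of participation, which the trial expects to differ by arm

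*Protocol*

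**What the plan says.** Protocol section 17.3 lists among its secondary during-treatment hypotheses "Incentive participants will receive a higher mean number of counseling hours per week than no incentive participants". The first hypothesis in the same list is "Incentive participants will have longer treatment retention than no incentive participants".

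The data behind the counseling hypothesis are described in three places:

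- Section 7 asks that clinics be "Able to provide records of counseling attendance by individual clients", or set up a system to obtain those data. This is attendance, not duration.
- Section 15.2 defines the data as "number of individual (15 minutes or more) and group counseling contacts per week for each study subject". Individual contacts have a 15-minute minimum. Group contacts have no stated length.
- Section 16.2, under Counseling utilization, lists two outcomes: "Total number of group and individual sessions received" and "Mean number of group and individual sessions per week during weeks of participation".

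Section 16.4 assigns t-tests to continuous summary variables, with regression if covariates are needed.

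**The concern.** Two things do not fit together.

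The first is the unit. The hypothesis is about hours, while everything collected or listed as an outcome is a count. If contact lengths are never recorded, no later analysis document can recover them. Counts are also not a safe stand-in for hours if the arms differ in their mix of individual and group contacts.

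The second is the denominator. The hypothesis is per week, and the only per-week outcome averages over the weeks in which a person participated. The arm may influence that number of weeks, and the protocol predicts that it will. Someone who leaves in week 3 is averaged over three weeks and someone who stays is averaged over twelve. If attendance thins out with time, keeping people longer lowers an arm's average even though they receive more counseling. At stake is whether the trial reports correctly if incentives raise or lower the uptake of counseling, one of the measures on which section 2 says the arms will be compared.

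**Working it through.** The protocol gives no session rate, standard deviation, effect size or power for counseling, so there is no stated figure to reproduce. The unit mismatch is settled by reading sections 7, 15.2, 16.2 and 17.3 together. The numbers below show what could follow from it. All attendance rates, contact lengths and retention figures are assumptions unless a source is given.

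**1. Sessions against hours.** Assume 1.2 individual + 0.5 group contacts a week with incentives and 0.8 + 0.7 in control. Sessions: 1.7 v 1.5, difference +0.2.

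- Individual 0.25 h, group 1 h: 0.30 + 0.50 = 0.80 v 0.20 + 0.70 = 0.90, difference -0.1 h.
- Individual 0.25 h, group 1.5 h: 0.30 + 0.75 = 1.05 v 0.20 + 1.05 = 1.25, difference -0.2 h.
- All contacts 1 h: 1.7 v 1.5, difference +0.2 h.

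The two units can disagree in sign, but need not.

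**2. Denominator, simple case.** Assume 60% of controls and 80% of incentive participants stay 12 weeks at 1.0 session a week. The others stay 3 weeks at *r* sessions a week.

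- Mean rate per week of participation: control 0.6 + 0.4*r*, incentive 0.8 + 0.2*r*. The difference is 0.2(1 - *r*).
- Mean total sessions: control 0.6 × 12 + 0.4 × 3*r*, incentive 0.8 × 12 + 0.2 × 3*r*. The difference is 2.4 - 0.6*r*.

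| *r* | Rate per participation week, control v incentive | Total sessions | Total / 12 |
|---|---|---|---|
| 1.5 | 1.20 v 1.10 | 9.0 v 10.5 | 0.75 v 0.875 |
| 1.0 | 1.00 v 1.00 | 8.4 v 10.2 | 0.70 v 0.85 |
| 0.5 | 0.80 v 0.90 | 7.8 v 9.9 | 0.65 v 0.825 |

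The rate reverses only when *r* exceeds 1, that is, when leavers attend more densely than stayers. At *r* = 1 it shows no difference although the incentive arm receives 1.8 more sessions per person.

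**3. Denominator, attendance falling over time.** Assume both arms have identical week-by-week attendance, starting at 2 sessions a week and falling 10% a week. A person who stays *T* weeks then averages 2(1 - 0.9^*T*)/(0.1*T*) per week of participation: 1.81 for *T* = 3 and 1.20 for *T* = 12. Longer stay alone lowers the average.

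For whole arms, the 75% v 40% completion contrast from the cited 24-week voucher study in section 3 is borrowed, with a constant weekly drop-out chance. Weekly persistence *p* is 0.75^(1/11) = 0.974 and 0.40^(1/11) = 0.920. With *q* = 0.9*p*, expected total sessions are 2(1 - *q*^12)/(1 - *q*) = 12.88 and 10.42. A simulation of 200,000 people per arm gave 12.86 v 10.42.

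| Simulated quantity | Incentive | Control | Difference |
|---|---|---|---|
| Mean weeks | 10.4 | 7.9 | +2.5 |
| Total sessions | 12.86 | 10.42 | +2.44 |
| Sessions per week of participation | 1.30 | 1.47 | -0.17 |
| Sessions / 12 | 1.07 | 0.87 | +0.20 |

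The range of the participation-week difference:

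- Equal attendance, same retention contrast: about 0 with no decline, -0.10 at 5% a week, -0.21 at 15%.
- Incentive attendance 10% higher, 10% decline: -0.04, while total sessions differ by +3.74.
- Smaller retention gaps (70% v 60%, 80% v 70%), equal attendance: about 0 to -0.06, with total sessions +0.4 to +1.4.
- Smaller gaps with 10% higher incentive attendance: positive throughout, +0.05 to +0.20.

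Sessions / 12 favoured the incentive arm in every scenario, in agreement with total sessions.

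**The case against.** The strongest reply is that section 16.2 already plans total sessions, the measure without the denominator problem, and that the hypothesis does not say which weeks it divides by. Both points are correct. A reader might infer that the trial has no usable comparison of counseling, and the documents do not support that. What remains is that the hypothesis is worded per week, and the one per-week outcome listed is the retention-dependent one. A detailed definition of weeks of participation can properly sit in a statistical analysis plan and is not counted as a gap here.

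It can also be said that the reversal comes from chosen inputs. That stands too. Nothing in the protocol shows that leavers attend more densely or that attendance declines. Participants enter after at least four weeks of maintenance, so study week 1 is not the start of treatment. The 75% v 40% contrast comes from cocaine-dependent outpatients over 24 weeks, not from a methadone clinic over 12.

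Total sessions and intensity while attending are different questions, and both are legitimate. The participation-week rate is therefore worth keeping. Step 3 shows, however, that it is not a clean measure of intensity when attendance changes over time.

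A reader might also infer that counselors at prize draws inflate contacts in the incentive arm, because section 11.5 says that, when it can be arranged, "these recovery pick events should take place in the presence of the study" participant's counselor. The documents do not establish this. The arrangement is conditional, section 12 lists it among possible roles to be settled locally, and section 15.2 counts counseling contacts, with a 15-minute floor for individual ones. A contact at a draw that does become 15 minutes of counseling is counseling received.

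**Conclusion.** The unit contradiction holds without any assumption: a hypothesis in hours cannot be tested from counts of contacts and sessions. The denominator point holds as a conditional one. The per-week outcome conditions on a post-randomisation quantity that the same section expects to be longer with incentives. It can understate or reverse a difference in total sessions if attendance falls over time or leavers attend more densely than stayers. It does not reverse when leavers attend no more densely, or in the simulation with no decline. Under the assumed scenarios with equal attendance, the distortion runs from about 0 to -0.21 sessions a week and is at most about -0.06 with the smaller retention gaps.

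The stronger statement, that the counseling comparison will come out with the wrong sign, is not supported. The outcome is secondary, and the primary analyses of stimulant use are unaffected.

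**What to change.** - In section 17.3, restate the counseling hypothesis in sessions instead of hours.
- Name total sessions in all randomised participants as the measure tested. Dividing by the 12 scheduled weeks, with zero sessions after leaving, is equivalent and keeps the per-week wording.
- In section 16.2, keep the mean per week of participation as a supportive description of intensity while attending.
- Optionally, add a sentence to section 15.2 that merely witnessing a prize draw is not a counseling contact.

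The cost is protocol wording, since the counts needed are already to be collected under section 15.2. There is a small downside: the tested measure combines retention with attendance intensity, so a difference would not show which of the two produced it. The retention analysis and the supportive rate help with that reading. If hours are what the investigators want, the alternative is to record the length of each contact, which adds to the tracking work at every clinic.
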